- To determine the variability of glucose excursion, level and peak and the recovery time in the three-hour postprandial period.
- To describe comparisons between all the above measurements and the variables of sex, age, disease duration, BMI, HbA1c, insulin dose/sensitivity and insulin regimen.
- To describe comparisons between all the above measurements and the glycaemic load and composition of the test and control meals.

Study design

This is a quantitative study. Dexcom CGM data will be collected for the period of recording. Participants will be asked to test three breakfast meals on two occasions and submit a postprandial questionnaire after each test meal to confirm it has been tested. The postprandial period will be three hours following the end of the breakfast test meal. The test meal recipes

will be provided by the chief investigator. The dietary composition of the meals has been analysed using the Nutritics dietary analysis programme (Nutritics, 2022). The glycaemic index and load of the meals is estimated from the Nutritics programme which uses available data from the international tables of glycaemic index and glycaemic loads (Atkinson *et al.* 2008; 2021). Most foods were based on average composition across different brands. For the added fibre bread used in test meal 3, an average of three known brands was used calculated by the chief investigator. The meals will be taken in the home environment with the food provided by the families. The participants will be asked to take the test meal on a day when their CGM reading is between 4-10mmol/l and when there has been no nocturnal hypoglycaemia on the night before the planned test. The participants will act as their own control. They will be asked to complete a postprandial questionnaire for control meals as well. The control meals will be their usual breakfast of choice. The study duration, commencing with the recruitment of the first participant and ending when data has been fully described, is anticipated to be two years.

Participants

Eligibility criteria

- Children and young people aged between 5-17 years
- Diagnosis of type 1 diabetes for a minimum of one year
- On multiple daily injections (MDI) together with carbohydrate counting or Continuous Subcutaneous Insulin Infusion (CSII) using either open or closed loop systems.
- Use Dexcom continuous glucose monitoring (CGM) on a regular basis
- Have a Dexcom Clarity account and use the Clarity App

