- Regularly eats a breakfast meal before midday
- Access to internet and email

Exclusion criteria

- Prescribed anti-hyperglycaemia agents *i.e.* Glucophage (Metformin) and or antidepressants.
- Any other medical conditions that may impact on the digestion and or absorption of nutrients, including coeliac disease and gastroparesis.
- Vegans
- Allergic or intolerant to the test meals
- Experiencing difficulties with food including diagnosed eating disorders
- Currently actively taking part in another research study

Recruitment

Paediatric diabetes dietitians, working across the UK, will be enrolled to help recruit participants and become principal investigators (PI) for their site. On enrolment, the chief investigator will provide the dietitians with all the relevant participant information sheets and consent forms as well as an Excel spreadsheet for entering the baseline information. The study documentation is presented in Appendices 1-9.

Sample size

The sample size power calculation is 64. This is based on using ANOVA repeated measures, within factors with four groups and measurements (3 test meals and control) with small effect size (0.15), P value 0.05 and power 0.80 and correlation among repeated measure of 0.5. The drop rate of clinical trials is often over 40%. Therefore, the aim is to recruit 90 participants to allow for this dropout rate and meet the sample size of 64. It may be possible to recruit this number of participants. There are approximately 29,000 children and young people living in the UK with T1D (Juvenile Diabetes Research Federation (JDRF), 2018). In the first phase of this study, 12 NHS sites were enrolled, and 96 children and young people were recruited to the study.

Methodology

Baseline data

In order to make comparisons between relevant variables and glucose levels, the following baseline data will be collected from the dietitians and sent to the chief investigator, along with the artificial identifier on the Excel spreadsheet as discussed earlier at the stage of recruitment of participants:

- Parent's email address
- Sex, date of birth and recent weight and height (for calculation of BMI and BMI centile) and date of when this was taken
- Date of diagnosis of T1D
- Last four HbA1c
- Total daily insulin dose (TDD)
- Insulin: carbohydrate ratios (ICR) and Insulin Sensitivity Factor (ISF)

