- Current insulin regimen - including the type of insulin prescribed and if applicable type of insulin pump i.e. open or closed loop system.

Run-in period

At recruitment the dietitians will be asked to arrange a review of the participants insulin regimen including the insulin to carbohydrate ratio's (ICR), insulin sensitivity factor (ISF) and basal background insulin doses/rates. The dietitian will be asked to inform the chief investigator when this has taken place. Participants will be asked to commence the test meals following this.

Glucose measurement

Data on interstitial glucose will be collected via Dexcom CGM. The Dexcom CGM data will be accessed by an NHS Highland research 'Clarity Clinic' with Dexcom CLARITY® Clinic Portal (Dexcom In, San Diego, CA, USA). The chief investigator is administrator of this clinic. Once the managing dietitian has obtained each participant's consent, the participant's parent's email address will be sent to the chief investigator along with the baseline information/data as described above. The chief investigator, as administrator of the Clarity Clinic account, will then invite the participant, via email, to be added to the clinic. Once the invite has been accepted, it will stand for the period of the recording i.e. until all the test meals and questionnaires have been completed. Once the participant has submitted their last questionnaire, they will be removed from the Dexcom CLARITY® Clinic Portal. They will be removed from the clinic portal if they withdraw from the study.

Test and control meals

Following the provision of CGM data and review of the insulin regimen by the diabetes team, participants will be randomised to test each of the three test meals on two separate occasions with a control meal (usual breakfast meal) for each test meal. Randomisation will be achieved using a Latin square randomisation. The tool used for this will be <http://www.jerrydallal.com/random/randomize.htm>. Randomisation will be done in a block of four.

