- Mean glucose
- Glucose variability (GV) % coefficient of variation (COV) target $\leq 36\%$
- Time in range (TIR) % and time spent between 3.9-10mmol/l
- Time above target (TAR) % and time spent $>10.1\text{-}<13.9\text{mmol/l}$ and $>13.9\text{mmol/l}$
- Time below range (TBR) % and time spent 3.0-3.8mmol/l and $<3\text{mmol/l}$

Target glucose levels:

- TIR - % of readings $>70\%$ or 16hr 48min
- TAR - % of readings $<25\%$ or $<6\text{hr}$ high and $<5\%$ 1hr 12min very high
- TBR- % of readings $<4\%$ or $<1\text{hr}$ low and $<1\%$ or $<15\text{min}$ very low

Primary outcome measure:

- Mean glucose (mmol/l) in the three-hour postprandial breakfast period calculated from the CGM measurements at 5 minutes intervals.

Secondary outcome measures – post prandial period:

- Number and percentage who had pre-prandial glucose in target, mean peak glucose level (mmol/l), mean time to peak (mins), mean time to recover (to pre-prandial levels) (mins) in the three-hour postprandial breakfast period
- TIR, TBR and TAR (% and time) in the three-hour postprandial breakfast period
- Comparisons of the above measurements between cohorts and breakfast test meal compositions.

Data analysis

This will be a mix of univariate, bivariate and multivariate analysis as this is best suited to describing, summarising and visualising these data. Outputs will include the distribution of glucose levels post-breakfast to determine the spread and dispersion of the data.

Safety considerations

Recruitment/consent

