Assent and parental consent will be obtained for the participants who are aged under 16 years. Where possible consent should be taken face to face. However, consent can be taken electronically. This will involve the dietitians meeting with the families either virtually or via telephone to go through the study and read through the consent form. As per the HRA/MRC Consent and Participant Information guidance, 'electronic methods for documenting consent can be considered to be in writing'. The dietitian should provide a copy of the signed consent form to the participant and this can be sent electronically. Electronic signature can be a simple electronic signature which can be a typed name (<http://www.hra-decisiontools.org.uk/consent/glossary>). Consideration will be given to those potential participants/families who are experiencing difficulties managing their condition, for example 'diabetes burnout'; poor glycaemic control or other stressors, for example, family difficulties, stress at school, for example, dealing with bullying or exam pressures. This will be minimised by recruiting via the managing dietitian who will have significant knowledge of the potential participant and who will be expected to discourage recruitment, if it is felt the family have enough to cope with. Those who are newly diagnosed will not meet the eligibility criteria as it is felt this would be unethical given the pressure they will be experiencing dealing with a new diagnosis of a chronic disease. Participants will not be asked to change their usual diabetes management. Participants will not be expected to eat the breakfast meal if it is something they do not like. Rather than adjusting their postprandial activities, participants will be asked to test the meals on days when they have less than 30minutes of exercise planned. The postprandial

period is three hours in order that most participants will be able to partake in their usual mid-morning snack as it is anticipated this will be more than three hours after the end of breakfast.

Personal data collection

Personal data as described above will be collected and will be securely managed. How this will be managed is described in the 'Data Management' section.

Burden on dietitians

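### Mean time to recover has no value for occasions still above their pre-prandial level at 180 min, and no rule scores, censors or counts them

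*Combined protocol and SAP*

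**What the plan says.** The list of secondary outcomes for the postprandial period includes "mean time to recover (to pre-prandial levels) (mins) in the three-hour postprandial breakfast period". The Objectives carry the same limit: "To determine the variability of glucose excursion, level and peak and the recovery time in the three-hour postprandial period". Study design starts the three-hour window at the end of the meal.

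The outcome is meant for comparison. The same list ends with "Comparisons of the above measurements between cohorts and breakfast test meal compositions", and Study design adds "The participants will act as their own control". Each test meal is taken on two occasions (Test and control meals).

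The reference level varies by occasion, because participants are to "take the test meal on a day when their CGM reading is between 4-10mmol/l". Under Glucose measurement, access to the CGM data does not stop at three hours: "it will stand for the period of the recording i.e. until all the test meals and questionnaires have been completed". The window itself is explained under Safety considerations, Recruitment/consent: the "period is three hours in order that most participants will be able to partake in their usual mid-morning snack".

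Data analysis names only univariate, bivariate and multivariate methods. Nowhere is there a rule for an occasion that has not returned to its pre-prandial level by 180 min, or for one that never rises above it.

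**The concern.** A plain mean of minutes needs a number for every occasion. Here an occasion has a number only if glucose returned to its starting level within 180 min, so whether a value is missing depends on the outcome itself, and the missing values are the slow ones. The limit comes from the outcome definition rather than the sensor. Later readings do not fill the gap as the plan is written, because the outcome is confined to three hours and a snack is expected afterwards.

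If unrecovered occasions are counted as 180, the result is a restricted mean, which is sound if labelled. If they are left out, each affected meal's mean describes only the occasions that recovered. With no rule, that choice could be made after the data are seen, and a reader could not tell which was used or how many occasions never recovered. That count is informative in its own right in a study of postprandial hyperglycaemia.

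**Working it through.** **Inputs.** From the documents: the 180-min window, two occasions per test meal, 64 children and "correlation among repeated measure of 0.5" (Sample size). That correlation was assumed for the repeated-measures ANOVA, not for recovery times, and is borrowed here. Assumed: log-normal recovery times, medians of 60 to 210 min, log-SD 0.3 to 0.5. The documents state no figure for recovery time, so there is none to reproduce.

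**Step 1: direction for one meal.** Let p be the share recovered by 180 min and m the mean among recoverers. Counting unrecovered occasions as 180 gives the restricted mean R = p·m + (1−p)·180. Hence R − m = (1−p)(180−m). This is positive whenever p < 1 and m < 180, without any distributional assumption. It is zero for a meal on which every occasion recovers.

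**Step 2: size for one meal.** For median M and log-SD s, let z = ln(180/M)/s. Then p = Φ(z) and m = M·exp(s²/2)·Φ(z−s)/p. With s = 0.5:

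| Median (min) | Recovered (%) | Recoverers' mean | Restricted mean | Shortfall (min) |
|---|---|---|---|---|
| 60 | 98.6 | 65.9 | 67.5 | 1.6 |
| 90 | 91.7 | 90.3 | 97.7 | 7.4 |
| 120 | 79.1 | 106.9 | 122.2 | 15.3 |
| 150 | 64.2 | 118.1 | 140.2 | 22.2 |
| 210 | 37.9 | 131.5 | 161.6 | 30.1 |

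Check at 120: (1 − 0.791) × (180 − 106.9) = 0.209 × 73.1 = 15.3. With s = 0.3 the shortfalls are 0.0, 0.9, 5.5, 12.6 and 20.6 min.

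**Step 3: gap between two meals.** This step assumes a complete-case paired analysis: the within-child difference among children with at least one recovered occasion on both meals. There are 64 children, two occasions per meal, s = 0.5, correlation 0.5 on the log scale and 12,000 simulated trials per scenario. Restricted gaps are exact.

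| Medians | Gap, recoverers only | Gap, restricted | Children lost (mean) | SE, recoverers only / restricted |
|---|---|---|---|---|
| 60/90 | 26.7 | 30.3 | 1.7 | 3.4 / 3.6 |
| 90/120 | 19.8 | 24.4 | 6.7 | 4.1 / 4.0 |
| 120/150 | 14.7 | 18.1 | 15.3 | 4.7 / 3.9 |
| 150/210 | 19.9 | 21.4 | 32.1 | 6.0 / 3.6 |

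The gap is understated by 1.5 to 4.6 min, less than one 5-minute CGM interval. The loss of precision is material only for the two slower pairs.

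**Step 4: sensitivity.** The grid is correlation 0.3, 0.5, 0.7 by log-SD 0.3, 0.4, 0.5 by the four median pairs, 36 scenarios in all. Restricted minus recoverers-only gap runs from +6.0 min (90/120, log-SD 0.5, correlation 0.3) to −5.3 min (150/210, log-SD 0.3, correlation 0.7). Mean children lost runs from 0.04 to 37.8 of 64.

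**The case against.** The plan does not commit to leaving unrecovered occasions out. Its wording is also compatible with a time capped at 180 min. That stands: the defect is an unspecified rule, and the bias is conditional on omission.

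A reader might infer that the study will lose children from this comparison. The documents do not support that. Saying that participants are their own control describes the design; it is not a complete-case rule, and no paired test is named. A mixed model would keep a child with no recovered occasion on one meal, though it would still face missingness that depends on the outcome.

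A reader might also infer that differences between meals will be systematically shrunk. The grid does not show that: the sign changes, and in the main setting the distortion is under 5 min. The largest losses of children come from the 150/210 pair, where only 30% to 38% of the slower meal's occasions recover. A much larger shrinkage appears if the comparison is made with the unrestricted mean (68.0 min for 150/210 at log-SD 0.5). However, the outcome is confined to three hours and does not claim to estimate that quantity, and the restricted mean shows the same compression.

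Finally, this is one item in a list of secondary outcomes in a largely descriptive study, and the other postprandial measures remain. That limits how much it matters. It does not supply the missing rule.

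**Conclusion.** The omission is certain from the text. So is the direction for any single meal with an unrecovered occasion, if observed times alone are averaged: the mean is too low by (1−p)(180−m) against the 180-min restricted mean. The size cannot be derived from the documents. On assumed log-normal times with log-SD 0.5, the per-meal shortfall is 1.6 to 30.1 min for medians of 60 to 210. Under a complete-case paired analysis that the plan does not name, the between-meal gap is distorted by about 6 min understated to 5 min overstated. If nearly all occasions recover, the effect is negligible.

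The primary outcome, mean glucose over three hours, and the sample size of 64 are untouched. The point should be settled before analysis because the repair is cheap and, at a median of 150 min and log-SD 0.5, the same data could be reported as 118 or 140 min.

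**What to change.** Under Secondary outcome measures, replace mean time to recover with two measures:

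- (a) the number and percentage of occasions back to the pre-prandial level by 180 min, by meal;
- (b) the restricted mean recovery time to 180 min, labelled as such. Time runs from the end of the meal, where Study design starts the window. Recovery is the first return to the pre-prandial level after a rise, and unrecovered occasions count as 180.

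Compare both between meals with a model that allows for repeated occasions within child. Because (b) piles up at 180, a time-to-event analysis censored at 180 min, again allowing for repeats, is an acceptable alternative.

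Report separately, by meal, the number of occasions that never rise above the pre-prandial level. Leave them out of (a) and (b), with a sensitivity analysis scoring them as 0 min. Flag occasions on which carbohydrate was taken for hypoglycaemia within the window, since it can alter the recovery time.

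The cost is rewording one secondary outcome and a standard analysis of CGM data already planned, with no extra data or participants. The downside is that a restricted mean compresses differences between slow meals (21.4 against 68.0 min unrestricted for medians 150/210, log-SD 0.5), so (b) must be read with (a).
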